Location of study conduct	
Each subject will participate in the study in the participating organization by which the subject is employed:
 
• SI National Institute of Phthisiology and Pulmonology named after F.G. Yanovsky.• Yuria-Pharm LLC.• Infuzia PJSC.• Institute Hyalual LLC.• Medical Center M.T.K. LLC.• InterChem SLC.• Diatom LLC. 
For the study the following facilities will be organized at each participating organization:
 
• Specially designated locations for material collection and conduction of rapid ELISA tests for the antibodies to COVID-2019.• Specially designated computerized places for questionnaires with assigned staff who organize the order and accuracy of the questionnaire conduct.
Duration of data collection	3 months.
Purpose of the study	To determine the relationship between the systematic use of prophylactics to prevent SARS, including COVID-2019, and the risks of incidence and serious complications of COVID-2019 among staff of participating organizations.
Study objectives	
• To investigate the incidence of COVID-2019 cases in participating organizations.• To investigate the severity of the COVID-2019 cases in participating organizations.• To explore the prevention methods used by staff members.• To determine the relationship between the used prevention methods and incidence of COVID-2019 among staff of participating organizations.

	
• To determine the relationship between the presence of comorbidities, such as bronchial asthma and COPD, and the incidence/severity of COVID-2019.• To determine the relationship between the COVID-2019 case and the course of comorbidities, such as bronchial asthma and chronic obstructive pulmonary disease (COPD).• To identify the relationship between different strategies and combinations of drugs used for prophylactics at any time from March 2020 and the risk of having a COVID-2019 case.• To identify the relationship between different strategies and combinations of drugs used for prophylactics at any time from March 2020 and the risk of having a severe COVID-2019 case.• To identify the relationship between different strategies and combinations of drugs used for prophylactics at any time from March 2020 and the risk of hospitalization of persons who had at least one COVID-2019 case.

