Study endpoints	
• The incidence of COVID-2019 cases in participating organizations.• The severity of the COVID-2019 cases in participating organizations.• Prevention methods of SARS, including COVID-2019, which were used by subject who had at least one COVID-2019 case.

	
Prevention methods of SARS, including COVID-2019, which were used by subject who did not have any COVID-2019 case.Relationship between the used prevention methods and incidence of COVID-2019 among staff of participating organizations.Relationship between the presence of comorbidities, such as bronchial asthma and COPD, and the incidence/severity of COVID-2019 case.Relationship between the COVID-2019 case and the course of comorbidities, such as bronchial asthma and chronic obstructive pulmonary disease (COPD).Relationship between different strategies and combinations of drugs used for prophylactics at any time from March 2020 and the risk of having a COVID-2019 case.Relationship between different strategies and combinations of drugs used for prophylactics at any time from March 2020 and the risk of having a severe COVID-2019 case.Relationship between different strategies and combinations of drugs used for prophylactics at any time from March 2020 and the risk of hospitalization of subjects who had at least one COVID-2019 case.
Study variables	
Demographic characteristics: age, gender.Anthropometric characteristics: body weight, height.Blood group.Number of people in the household.Lifestyle: the presence of bad habits, physical activity, diet.Medical history: comorbidities, their treatment.Prevention methods of SARS, including COVID-2019, currently used by the subject.Number of COVID-2019 cases, which subject had.Characteristics of the disease case, its treatment.

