	
Prevention methods of SARS, including COVID-2019, which were used by subject who had at least one COVID-2019 case.Prevention methods of SARS, including COVID-2019, which were used by subject who did not have any COVID-2019 case.Amount of costs spent on prevention and treatment of SARS, including COVID-2019.Relationship between different strategies and combinations of drugs used for prophylactics at any time from March 2020 and the risk of having a COVID-2019 case.Relationship between different strategies and combinations of drugs used for prophylactics at any time from March 2020 and the risk of having a severe COVID-2019 case.Relationship between different strategies and combinations of drugs used for prophylactics at any time from March 2020 and the risk of hospitalization of subjects who had at least one COVID-2019 case.
Inclusion criteria	Subjects who meet all the inclusion criteria will be included in the study: 
The subject gave the consent to participate in the study and signed the consent to processing of personal data.The subject aged 18 years and older.The subject is employed by one of the participating organizations.
Exclusion/withdrawal criteria	The nature of the study does not provide for withdrawal criteria. The subject may not be included in the study due to non-compliance with the inclusion criteria or due to force majeure.
Calculation of sample size	Not applicable as it is exhaustive study. Participating organizations undertake to organize the involvement in the study of at least 95% of persons employed by participating organizations.

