Study limitations	
Persons, who were employed by one of the participating organizations from March 1, 2020, but who do not have employment relations with the participating organizations during the study period or persons who are on maternity leave, will not be included in the study.
 
Another study limitation is duration of data collection (due to long-term data collection there is a difference in the duration of action of the exposure factor).
 
The retrospective study design has limitations on the completeness and accuracy of the data provided by the study subjects.
 
There may be difficulties in filling in the missing data.
 
Certain relationships can be difficult to describe.
 
The direction of the relationship cannot be determined for all relationships (there may be an inverse relationship).
 
Potential data distortion may be due to the subject selection; use of an electronic data collection system; possible low computer literacy of some subjects; lack of data verification and query generation.
 
The completeness and correctness of the description of available medical documentation for fatal cases of COVID-2019 depends on the amount of information provided and its quality. Conclusions from it cannot be extended to other population members.

-------------------	---

Statistical analysis plan

In the context of this data analysis, all the main steps from the primary data to the results of the study will be described separately in the Statistical Analysis Plan.

This study is not intended to accept or reject pre-defined hypotheses, thus statistical analysis will mainly be descriptive.

All types of analysis will be done for the entire available study population with available data.

If there is a sufficient amount of data in the subpopulations, a separate statistical analysis will be performed.

No conditional calculation methods will be applied to the missed values.

The statistical generalization will consist of frequency tables of categorical variables (number, %).

For metric variables, descriptive statistics (number of subjects with available observations, number of missed values, mean, standard deviation, median, 25th and 75th percentiles, minimum and maximum) will be presented in tabular form.

Statistical conclusions will be used to assess the potential relationship between the identified variables and the incidence / severity of COVID-2019.

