The relationship between the subject's characteristics and the variables of interest will be assessed using a one-dimensional and multidimensional (polynomial) logistic regression model for variables, which have no more than 20% omitted data.

The final model will be selected with a view to minimizing the Akaike information criterion value.

2×2 tables, χ^2 -square were used for calculations of odds ratios.

Rough odds ratios and adjusted odds ratios with corresponding 95% confidence intervals and p-values will be generated and presented for both one-dimensional and multidimensional logistics models.

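### Drug exposure in three risk endpoints is not closed at illness onset, so use begun after an illness can count as exposure for it

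*Combined protocol and SAP*

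**What the plan says.** Under Study endpoints, exposure is defined three times by one open window: "drugs used for prophylactics at any time from March 2020 and the risk of having a COVID-2019 case", then "at any time from March 2020 and the risk of having a severe COVID-2019 case", then hospitalisation among subjects with at least one case. The same three items recur under Study objectives ("at any time from March 2020 and the risk of hospitalization of persons who had at least one COVID-2019 case") and under Study variables.

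The Statistical analysis plan section says that relationships "will be assessed using a one-dimensional and multidimensional (polynomial) logistic regression model", and that 2×2 tables with chi-square "were used for calculations of odds ratios". "Rough odds ratios and adjusted odds ratios with corresponding 95% confidence intervals and p-values will be generated" for both kinds of model. No time element is attached to any of these.

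The same section states that "all the main steps from the primary data to the results of the study will be described separately in the Statistical Analysis Plan". That document was not supplied, and neither was the questionnaire.

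Three other places bear on timing:
- Methodology describes a questionnaire block for cases only, which covers prophylactics but does not say whether before or after the illness.
- Study variables lists current prevention methods separately from methods used by cases and by non-cases, and also lists "Number of COVID-2019 cases, which subject had". It does not say which case an exposure belongs to.
- Study limitations admits that some relationships may run in the inverse direction and that duration of exposure differs.

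**The concern.** The stated purpose is to relate systematic prophylactic use to the risk of COVID-19 and its serious complications. Use that began after an illness cannot have affected that illness. The window opens in March 2020, and nothing in the supplied text closes it at onset.

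An odds ratio away from 1 could then reflect a drug effect or a change in behaviour after illness. People who have been ill may see less need for prophylaxis, or more. Adjusting for age, sex or comorbidity does not separate these explanations. If uptake was gradual, a real effect would also be diluted, because part of the users' illness experience came before they started.

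**Working it through.** The plan has no figure to reproduce: it gives 3443 as a head count and treats sample size as not applicable. The documents contain no uptake, start dates or onset dates, so every input below is an assumption: uptake p = 0.5, a 12-month window, and starts spread evenly over the first w months.

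**1. Open window, no drug effect.** Onsets are spread evenly over 12 months.
- Cases already using at onset: pre = p(1 − w/24).
- Natural later starting among those not yet using: q = (p − pre)/(1 − pre).
- If illness multiplies later starting by f, ever-use in cases is pc = pre + (1 − pre)·q·f.
- OR = [pc/(1 − pc)] / [p/(1 − p)].

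For w = 12: pre = 0.25 and q = 0.25/0.75 = 0.333. With f = 0.5, pc = 0.25 + 0.75 × 0.333 × 0.5 = 0.375, so OR = 0.375/0.625 = 0.60. With f = 1.5, pc = 0.625 and OR = 1.67.

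| Starts over first w months | f = 0.5 | f = 1 | f = 1.5 | Exposed cases who began after onset at f = 1 (w/24) |
|---|---|---|---|---|
| 12 | 0.60 | 1.00 | 1.67 | 50% |
| 6 | 0.78 | 1.00 | 1.29 | 25% |
| 3 | 0.88 | 1.00 | 1.13 | 12.5% |
| 1 | 0.96 | 1.00 | 1.04 | 4.2% |

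For hospitalisation among cases, the same formula applies with f as the ratio of later starting in hospitalised to other cases.

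A second model is milder. It uses a constant rate of starting, and illness halves or doubles that rate. Ever-use in cases is 0.402 or 0.639 against 0.50 in non-cases, so OR = 0.67 or 1.77.

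**2. Open window, true rate ratio 0.5, behaviour unchanged.** Assume 20% incidence in non-users, so the cumulative hazard is H = −ln 0.8 = 0.2231. A user who starts at fraction u of the year has risk 1 − exp(−Hu − 0.5H(1 − u)). Averaged over u from 0 to 1, this is 0.1537, so OR = (0.1537/0.8463)/(0.2/0.8) = 0.73. For w = 6, 3 and 1 the OR is 0.60, 0.53 and 0.49. If all users had started on day one, the risk would be 0.1056 and the OR 0.47.

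**3. Pre-onset use with index months.** Each non-case receives a month drawn from the case-onset months, and same-month starts are unexposed in both groups. Simulated with N = 3443 and w = 12, 6, 3, 1, the median OR is about 1.00 throughout with no effect. With a rate ratio of 0.5 it is 0.53, 0.53, 0.52, 0.50. Person-months stratified by calendar month (w = 12) give 1.00 and 0.51, both over the full 12 months and with a month-10 cut-off.

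**4. Pre-onset use among cases, unadjusted.** With w = 12, the chance of having started by onset month m is p·m/12. Suppose there is no drug effect and other cases have mean onset at month 6 (25.0%):
- Hospitalised cases at month 7: 29.2%, OR = (0.292/0.708)/(0.25/0.75) = 1.24.
- Month 8: 33.3%, OR = 1.50.
- Month 9: 37.5%, OR = 1.80.

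The open window gives 1.00 in all three if behaviour is unchanged. Within one onset month the chance of prior use is equal in both groups, so stratifying by onset month restores 1.00. The same arithmetic applies if severe cases are compared with non-cases whose index months come from all cases.

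**The case against.** The strongest reply has four parts.

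*The rule may exist elsewhere.* This is a synopsis (version 0.2) that defers the main steps to a separate SAP. March 2020 may only open the recall period, and that SAP could close it at onset without contradicting the endpoint wording. The case-only block and the separate listing of current use suggest, without proving, that illness-related use is recorded apart. This stands, and makes the point conditional.

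*Bias is possible, not shown.* Also true. With unchanged behaviour the null odds ratio is 1.00, and the multipliers above have no basis in the documents. If the undated provision of prophylactic tools to staff (Justification of study) came early and all at once, the distortion is small.

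*It is disclosed, and the analysis is called mainly descriptive.* The limitation is general and no analysis step follows from it. Odds ratios with p-values are still planned for endpoints worded as risk.

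*Simply restricting to pre-onset use can do harm.* This is correct for comparisons among cases (step 4), and onset month must then be handled. Restricting to the first case could also lose a later severe or hospitalised one.

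A reader might go further and infer that the plan makes a useless drug look protective, by setting pre-illness use in cases against whole-window use in non-cases. In the step 1 model that would give pre/(1 − pre) = 0.25/0.75 = 0.33 for w = 12. No section states such a comparison: the written window is the same for both groups. The case-only block merely leaves room for it.

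**Conclusion.** The point holds in conditional form. As worded, the three endpoints let use begun after an illness count as exposure for it, and the planned odds ratios do not prevent this. Whether it will happen depends on a SAP and a questionnaire that were not supplied.

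The gap in the wording is certain; the direction and size of any bias are not. With 50% uptake spread over 12 months, the null odds ratio runs from 0.60 to 1.67 for the two behavioural changes tried, and a rate ratio of 0.5 shrinks to about 0.73. With starts confined to the first month the figures are 0.96 to 1.04, and 0.49. The documents do not support a claim that the bias is present, or that it favours the drugs. The timing rule should be fixed before the odds ratios are read as risk.

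**What to change.** In the three risk analyses, count only use begun before onset of the case being analysed.

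- **Any case, and severe case if compared with non-cases.** Either give each non-case an index month drawn from the onset months of the outcome group analysed (all cases, or severe cases), with same-month starts unexposed in both groups; or analyse person-months with time-updated exposure and calendar month up to a common cut-off.
- **Hospitalisation, and severity among cases.** Use pre-onset use, and adjust for or stratify by calendar month of onset.
- **Repeat cases.** State which case is used when a subject had more than one, so that a later severe or hospitalised case is not dropped unreported.
- **Data.** Confirm that the electronic case report form holds month of drug start and month of onset, plus month of stopping if use is to be classed as systematic. Add them if absent.
- **Missing onset.** Report how many cases or antibody-positive subjects lack an onset month, with a sensitivity analysis.
- **Reporting.** Keep ever-use and current use as descriptive associations without time order.
- **Wording.** If the separate SAP already sets a timing rule, align the endpoint wording with it.

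Cost: no extra subjects or visits. If the months are already collected, only definitions and analysis change; otherwise a few fields are added. Recalled months will be imprecise, subjects without an onset month leave these models, and same-month ties slightly dilute a real effect (0.53 against 0.51 with exact dates, for w = 12).

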Project code	EpidProtect-21
Study title	Exhaustive, cross-sectional, non-interventional, multicenter retrospective epidemiological study of the COVID-2019 incidence and prevention methods of SARS, including COVID-2019, among staff of participating organizations.
Version of Synopsis	0.2, 15.02.2021.
Justification of study	
Coronaviruses are a large family of viruses that might cause illness in animals or humans. SARS-CoV-2 is an enveloped, single-stranded RNA virus of the β genus. It can cause respiratory illness named COVID-19, the severity of which varies from asymptomatic to severe, and which can lead to the patient's death or long-term consequences (so-called post-COVID syndrome). The virus has spread globally and been declared a Public Health Emergency of International Concern by WHO in January 30, 2020.
 
The first case of COVID-19 in Ukraine was detected in early March, 2020. 1273475 cases of the disease have been registered in Ukraine as at February 15, 2021.
 
Quarantine restrictions and other anti-epidemic measures established in Ukraine and their results are the subject of wide debate.
 
Own anti-epidemic measures, in addition to those established by the Government, have also been implemented by numerous representatives of the public sector, non-governmental organizations and business.
 
The company management of the participating organizations decided to provide their staff with prophylactic tools and recommendations for COVID-19 prevention.
 
The study aims to identify the incidence, characteristics of cases and their relationship with the preventive measures used.

Study design	Exhaustive, cross-sectional, non-interventional, multicenter retrospective epidemiological study, case study.
Number of subjects	3443 subjects.

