Methodology	
Each subject will be assigned an individual number, which will be used for conduction of a rapid ELISA test for the antibodies to COVID-2019. Subjects will be notified of the test results.
 
The questionnaires will be conducted when the subject enters the data in the electronic case report form after signing the consent to processing of personal data.
 
For the purposes of analysis, the subject enters his individual number in the questionnaire, as well as number of a rapid ELISA test for antibodies to COVID-2019 and its result. The entered data will be compared with the databases which contain the results of rapid ELISA tests.
 
The questionnaire includes questions related to the main risks and protective factors of the COVID-2019 disease: demographic, anthropometric data, lifestyle data, prophylactics methods, subject's costs spent on COVID-2019 prophylactics.

	
For subjects who had the COVID-2019 case, a separate block of questionnaire was created to collect data on prophylactics, treatment of COVID-2019 case, the course of the disease and the consequences of the disease case, as well as costs spent on COVID-2019 treatment.
 
The completeness of entered data in the electronic case report form will be controlled by specially designated authorized persons in each participating organization, who were designated by the person responsible for conducting the study in each participating organization.
 
The correctness of data entered in the electronic case report form will be controlled by remote monitoring.
 
The questionnaire cannot be completed until all required fields of the case report form have been completed.
 
A structured description of the available medical documentation for fatal cases of COVID-2019 will be conducted separately.
 
Demographic, anthropometric data, lifestyle data, prophylactics methods, treatment of COVID-2019, the course of the COVID-2019 case will be described.

Duration of each subject's participation in the study	1,5-2 hours.
Visit schedule	
Visit 1. Conducting of a rapid ELISA test.
 
Visit 2. Online questionnaires among staff of participating organizations.

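### No pre-illness reference date is stated for comorbidities, weight and lifestyle, which are collected once after any past COVID-19 case, so changes caused by the illness can enter the models as predictors

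*Combined protocol and SAP*

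**What the plan says.** The Study design row describes the study as "Exhaustive, cross-sectional, non-interventional, multicenter retrospective epidemiological study, case study". The Visit schedule has two contacts: a rapid antibody test, then "Visit 2. Online questionnaires among staff of participating organizations". Participation lasts 1.5 to 2 hours, so nothing is measured earlier or later.

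Study variables lists body weight and height, "Lifestyle: the presence of bad habits, physical activity, diet" and "Medical history: comorbidities, their treatment". None of these has a time point. Other items in the same synopsis do: prophylactic drug strategies are tied to the period since March 2020, and one prevention item refers to current use.

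Methodology describes an extra questionnaire block for subjects who had COVID-19. It covers prophylactics, treatment, course, consequences and costs. Pre-illness weight, lifestyle and comorbidity are not among its listed contents.

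One endpoint is "Relationship between the presence of comorbidities, such as bronchial asthma and COPD, and the incidence/severity of COVID-2019 case". The next endpoint runs the other way, from COVID-19 to the course of asthma and COPD.

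The Statistical analysis plan section relates subject characteristics to the outcomes by univariable and multivariable logistic regression. The stated conditions are at most 20% missing data per variable and selection by lowest AIC. Study limitations says that direction cannot be established for every relationship and that some may be inverse.

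**The concern.** A predictor of COVID-19 incidence or severity should describe the subject before the illness. Here the information is gathered afterwards, and nothing in the plan separates earlier status from later change.

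This matters most for the asthma/COPD endpoint. A respiratory diagnosis made during or after the COVID-19 work-up could be counted as a comorbidity that was already present. An association would then arise from the illness itself. Because the plan also studies COVID-19 as a cause of change in these diseases, it needs to know to which side of the illness a diagnosis belongs. If onset is not collected, analysts cannot recover it later.

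The same applies to weight, smoking, activity and diet, all of which may shift after illness. AIC rewards fit, so it can favour a covariate because the illness changed it.

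**Working it through.** **Timing.** The first Ukrainian case was in early March 2020, the synopsis is dated 15 February 2021, and data collection lasts 3 months. If collection starts near the synopsis date (an assumption), it ends around mid-May 2021. The gap between illness and questionnaire can then reach about 14 months.

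**Plan's own figure.** There is none to reproduce. The number of subjects is "3443 subjects", a staff count, and the sample size calculation is "Not applicable as it is exhaustive study". The plan gives no comorbidity prevalence and no rate of new diagnosis, so every rate below is an assumption.

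**Asthma/COPD against incidence.** Let p be the true pre-illness prevalence, equal in cases and non-cases (true odds ratio 1). Let d1 and d0 be the shares of cases and non-cases without the condition who are newly diagnosed after March 2020.

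- Recorded prevalence in cases: q1 = p + (1 - p) × d1
- Recorded prevalence in non-cases: q0 = p + (1 - p) × d0
- Apparent OR = [q1/(1 - q1)] / [q0/(1 - q0)]

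With d0 = 0.003 and d1 = 0.01 or 0.03:

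| p | q0 | q1 (d1 = 0.01) | OR | q1 (d1 = 0.03) | OR |
|---|---|---|---|---|---|
| 0.04 | 0.04288 | 0.0496 | 1.16 | 0.0688 | 1.65 |
| 0.06 | 0.06282 | 0.0694 | 1.11 | 0.0882 | 1.44 |
| 0.08 | 0.08276 | 0.0892 | 1.09 | 0.1076 | 1.34 |

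For p = 0.06 and d1 = 0.03: (0.0882/0.9118) / (0.06282/0.93718) = 0.0967/0.0670 = 1.44.

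**Would it stand out from chance?** Take N = 3443 and an assumed 20% case share: 688.6 cases and 2754.4 non-cases. By Woolf's formula, SE(log OR) = √[1/(n1·q1) + 1/(n1(1 - q1)) + 1/(n0·q0) + 1/(n0(1 - q0))], where n1 and n0 are the numbers of cases and non-cases. At p = 0.06:

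- OR 1.11: SE 0.169, 95% CI 0.80-1.55.
- OR 1.44: SE 0.156, 95% CI 1.06-1.96. At a 10% case share the interval is 0.97-2.15.

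**A common, changeable habit.** Suppose 30% had the habit before illness, the true OR is 1, and only cases change. If a share c of the cases with the habit give it up, q1 = 0.30 × (1 - c) and q0 = 0.30.

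- c = 0.05: OR 0.93
- c = 0.10: OR 0.86
- c = 0.20: OR 0.74, 95% CI 0.61-0.89 at a 20% case share

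The distortion therefore runs from negligible to material, and the documents do not say where in that range the study lies. Severity, hospitalisation and the adjusted prophylaxis odds ratios were not calculated: the plan names no adjustment set, so there is no specified model to work from.

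**The case against.** The strongest reply is that this is a synopsis. The questionnaire wording is not in it, and the steps from raw data to results are deferred to a separate analysis plan. A one-line variable list does not prove that the form lacks dates. Comorbidities are labelled as medical history, the endpoint on the course of asthma and COPD needs some before-and-after information, and the case block collects consequences, where new diagnoses might be placed. The plan does not call these variables baseline, describes its analysis as mainly descriptive, and discloses possible inverse relationships.

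Much of this stands. A reader might infer that illness-caused changes do enter the models. The documents do not support that; they show only that nothing stated prevents it. A reader might also infer that adjustment makes the prophylaxis odds ratios worse, or that the distortion is greatest for severe and hospitalised cases. Both are plausible, but neither is shown. Age, gender, height and blood group are in practice unaffected.

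The disclosure does not settle the matter. It names no variable and offers no remedy, although for a comorbidity the order of events can be asked with a date. The descriptive label also sits beside a commitment to adjusted odds ratios with confidence intervals and p-values.

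**Conclusion.** The concern holds as an uncontrolled risk, not as a demonstrated error. There is one collection point after any past case, no stated pre-illness reference date for comorbidity, weight or lifestyle, and no timing rule for model entry. The clearest exposure is the endpoint relating asthma/COPD to incidence and severity.

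For incidence, a true odds ratio of 1 would appear as about 1.09-1.65. This rests wholly on assumed new-diagnosis rates of 1-3% in cases and 0.3% in non-cases, and on 4-8% prevalence. The low end could not be told from chance in a study of this size; the high end could look like a finding. The true size is unknown, and no figure is offered for severity or for the adjusted prophylaxis odds ratios.

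**What to change.** - Add month and year of first diagnosis for asthma, COPD and other comorbidities.
- In the main analysis, count as predictors only diagnoses made before one common date for all subjects, 1 March 2020. A common date keeps cases and non-cases comparable, and it also works for antibody-positive subjects who have no recognised illness date.
- Report later diagnoses separately, as possible consequences when they follow a COVID-19 case.
- Ask weight and smoking for the same date where feasible.
- Run a sensitivity analysis that leaves weight, habits, activity and diet out of the adjusted models.
- If the electronic form can no longer be changed, keep the sensitivity analysis and state the limitation variable by variable.

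The cost is one extra date field, rewording of a few items and some analysis-plan text. There are two drawbacks. Recall of status a year or more back is imperfect and may differ between cases and non-cases. A comorbidity diagnosed after 1 March 2020 but before infection would also be misclassified as absent.

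### The synopsis lists no measure of workplace exposure and does not name employer as a covariate, so the adjusted odds ratios for prophylaxis and COVID-19 incidence may be confounded in either direction

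*Combined protocol and SAP*

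**What the plan says.** The Purpose and Study objectives sections ask how prophylaxis relates to the risk of having COVID-19, of a severe case, and of hospitalization among those who had a case. The Statistical analysis plan section promises crude and adjusted odds ratios with 95% confidence intervals and p-values from logistic models, with the final model chosen by AIC. It names no confounder set.

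The Study variables section lists "Demographic characteristics: age, gender", weight and height, blood group, "Number of people in the household", "Lifestyle: the presence of bad habits, physical activity, diet", comorbidities and their treatment, prevention methods, number and characteristics of cases, and costs. The Methodology section describes the form in similar terms: "The questionnaire includes questions related to the main risks and protective factors of the COVID-2019 disease: demographic, anthropometric data, lifestyle data, prophylactics methods", followed by costs and a separate block for people who had a case. Neither section mentions job role, patient contact, or on-site versus remote work.

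The Location of study conduct section names seven organizations. They include a phthisiology and pulmonology institute and "Medical Center M.T.K. LLC" alongside other companies. Each subject takes part at their own employer, so employer is known, but it is not listed as a variable or covariate. The Justification section says that management chose to supply staff with preventive products and advice. The Study limitations section covers recall, selection, data quality and reverse direction of association. It does not mention unmeasured confounding.

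**The concern.** Workplace contact plausibly affects the chance of infection. It may also affect which prophylactics a person is given or chooses, since provision was partly employer-led and the sites appear, by name, to mix clinical and non-clinical work. A factor that acts on both sides of the main comparison confounds it. AIC can choose only among recorded variables, and it chooses for fit, not for control of confounding. Household size is the only listed variable that directly reflects opportunity for contact, and it covers the home only.

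At stake is the study's central result. If prophylaxis users have more workplace exposure, a real protective association could be weakened or hidden. If they have less, an apparent benefit could arise from nothing. Because the study is a near-census of staff, such a bias could come with a fairly narrow confidence interval.

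**Working it through.** **Plan figure to reproduce.** None. The sample size is given as "3443 subjects" and its calculation as "Not applicable as it is exhaustive study", with a target of "at least 95% of persons employed by participating organizations". No event rate, effect size or exposure prevalence is stated. Apart from N = 3443, every input below is an assumption.

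**Step 1: risk-ratio scale.** For a binary unmeasured exposure that multiplies infection risk by R, with prevalence p1 in one group and p0 in the other:

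bias factor = [1 + p1(R − 1)] / [1 + p0(R − 1)]

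With p0 = 0.20:

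| R | p1 = 0.40 | p1 = 0.50 | p1 = 0.60 |
|---|---|---|---|
| 1.5 | 1.20/1.10 = 1.09 | 1.25/1.10 = 1.14 | 1.30/1.10 = 1.18 |
| 2 | 1.40/1.20 = 1.17 | 1.50/1.20 = 1.25 | 1.60/1.20 = 1.33 |
| 3 | 1.80/1.40 = 1.29 | 2.00/1.40 = 1.43 | 2.20/1.40 = 1.57 |

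- Exposure commoner in users: a true risk ratio of 0.70 appears as 0.70 × 1.09 = 0.76 at the mild end, 0.70 × 1.25 = 0.875 at R = 2 with 50% vs 20%, and 0.70 × 1.43 = 1.00 at R = 3 with 50% vs 20%.
- Exposure commoner in non-users: the factors invert to between 1/1.57 = 0.64 and 1/1.09 = 0.92. With 50% vs 20%, no effect appears as 1/1.25 = 0.80 (R = 2) or 1/1.43 = 0.70 (R = 3).

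**Step 2: odds-ratio scale, which the plan reports.** Set the true prophylaxis odds ratio to 1 and split the 3443 subjects equally between users and non-users. Let baseline risk be 20%, the exposure odds ratio 3, and exposure be present in 20% of users and 40% of non-users.

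- Unexposed odds = 0.20/0.80 = 0.25. Exposed odds = 0.75, so exposed risk = 0.75/1.75 = 0.429.
- Risk in users = 0.2 × 0.429 + 0.8 × 0.20 = 0.246.
- Risk in non-users = 0.4 × 0.429 + 0.6 × 0.20 = 0.291.
- Spurious odds ratio = (0.246/0.754)/(0.291/0.709) = 0.79, Woolf 95% CI 0.68 to 0.92. The probability of p < 0.05 is 0.86.

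For the same 20% vs 40% imbalance and baseline risks of 10-30%, the spurious odds ratio is 0.92 at exposure odds ratio 1.5, 0.86-0.87 at 2, and 0.78-0.80 at 3. With the imbalance reversed it is 1.09 to 1.28. Adding extreme imbalances (10% vs 50% either way) widens the range to about 0.61 to 1.63.

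**Step 3: a mild case.** With exposure odds ratio 1.5 and 20% of users vs 30% of non-users exposed, the spurious odds ratio is about 0.96. The probability of p < 0.05 is 0.06 to 0.08, barely above the nominal 0.05.

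**Step 4: what adjustment would cost.** A three-level work setting needs 3 − 1 = 2 parameters and seven employers need 7 − 1 = 6, so 8 in all.

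**The case against.** **The item may exist.** A reader might infer that work setting is definitely not collected. The documents do not support that. They are a synopsis, the questionnaire is not included, and the Methodology list is a summary: it omits blood group and household size, which the Study variables section lists. Prevention methods are undefined and could include remote work. The analysis steps are also deferred to a separate plan. What can be said is that the item is not listed.

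**The information may be recoverable.** A reader might also infer that the gap is permanent. Every subject is a current employee with an individual number, so linkage to personnel records may still be possible.

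**The size is assumed.** No document gives the strength of workplace exposure, its imbalance or its direction. The Justification section speaks of staff in general, without distinguishing roles, so supply may have varied mainly by employer, which is known. The figures above describe the total imbalance between users and non-users, not what would remain after adjustment for employer. A claim that a major confounder is hiding or creating an effect therefore goes beyond the text. Employer adjustment alone would still not separate patient-facing from office staff, or on-site from remote staff, within one organization.

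**Severity and hospitalization differ.** Workplace exposure is a plausible cause of infection. The documents give no reason to think that it confounds severity or hospitalization among people already infected, and eight extra parameters could be too many if events are few. This stands, and it limits the remedy.

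**The analysis is mainly descriptive.** The plan disclaims hypothesis testing and warns that associations may run in reverse. That softens the consequence, but the stated purpose and the adjusted odds ratios still invite a reading about protection.

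**Conclusion.** The point holds for COVID-19 incidence, provided that the full questionnaire does not already record work setting. The listed variables and questionnaire domains contain no measure of workplace exposure, and employer is not a named covariate, so the planned adjustment leaves a plausible confounder uncontrolled. Under the assumed inputs the distortion is a factor of about 1.09 to 1.57 or its inverse. It is close to nothing when the imbalance and the exposure effect are small. Neither direction nor size can be settled from the documents. The change is worth making because it is cheap and bears on the main question, not because a large bias has been shown.

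**What to change.** 1. Check the full questionnaire. If work setting is absent, add one required eCRF item, or link from personnel records by individual number: main work setting since March 2020 (direct patient contact / on-site without patient contact / mainly remote).
2. List work setting and employer under Study variables.
3. Keep both in the adjusted models for the risk of having a COVID-19 case, regardless of AIC.
4. In the severity and hospitalization models, include them only if the number of events allows, for example as a sensitivity analysis.
5. If the item cannot be obtained, adjust for employer and name residual occupational confounding under Study limitations.

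Cost: a slightly longer form, or a linkage step; a coarse category, self-reported if taken from the form; and up to eight extra parameters in each model that carries both terms.
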